5.0 STUDY POPULATION

5.1 Sample Size

Approximately 20-25 subjects will be enrolled.

5.2 Tissue Procurement Inclusion Criteria:

Subjects will be eligible for tissue procurement for the Vigil manufacturing process, if they meet all of the following criteria:

- 1. Histologically confirmed Stage IIIb, IIIc or IV high-grade papillary serous, clear cell, or endometrioid ovarian, fallopian tube or primary peritoneal carcinoma
- 2. Age \geq 18 years.
- 3. Estimated survival \geq 6 months.
- 4. ECOG Performance Status ≤ 1
- 5. Metastatic disease
- Planned standard of care surgical procedure (e.g., tumor biopsy or palliative resection or thoracentesis) and expected availability of a cumulative soft-tissue mass of ~10-30 grams tissue ("grape" to "golf-ball" size) or ascites fluid estimated volume ≥ 500mL (from a primary or secondary paracentesis, yielding in a high volume of tumor cells) for immunotherapy manufacture.
- 7. Tumor intended for immunotherapy manufacture is not embedded in bone and does not contain luminal tissue (e.g. bowel, ureter, bile duct).
- 8. Ability to understand and the willingness to sign a written informed protocol specific consent for tissue harvest or a parental/guardian informed consent and pediatric assent when appropriate.

5.3 Tissue Procurement Exclusion Criteria:

Subjects meeting any of the following criteria are not eligible for tissue procurement for the Vigil manufacturing:

- Medical condition requiring any form of chronic systemic immunosuppressive therapy (steroid or other) except physiologic replacement doses of hydrocortisone or equivalent (no more than 30 mg hydrocortisone or 10 mg prednisone equivalent daily) for < 30 days duration.
- Known history of other malignancy unless having undergone curative intent therapy without evidence of that disease for ≥ 3 years except cutaneous squamous cell and basal cell skin cancer, superficial bladder cancer, in situ cervical cancer or other in situ cancers are allowed if definitively resected.

- 3. Brain metastases unless treated with curative intent (gamma knife or surgical resection) and without evidence of progression for ≥ 2 months.
- 4. Any documented history of autoimmune disease with exception of Type 1 diabetes on stable insulin regimen, hypothyroidism on stable dose of replacement thyroid medication, vitiligo, or asthma not requiring systemic steroids.
- 5. Known HIV or chronic Hepatitis B or C infection.
- 6. Known history of allergies or sensitivities to gentamicin.
- 7. History of or current evidence of any condition (including medical, psychiatric or substance abuse disorder), therapy, or laboratory abnormality that might confound the results of the study, interfere with the patient's participation for the full duration of the study, or is not in the best interest of the patient to participate, in the opinion of the treating Investigator.
- 8. Receipt of the last dose of anti-cancer therapy (chemotherapy, immunotherapy, endocrine therapy, targeted therapy, biologic therapy, tumor embolization, monoclonal antibodies, other investigational agent) less than 21 days prior to tissue procurement.

5.4 Study Enrollment Inclusion Criteria

Subjects will be eligible for registration into the trial if they meet all of the following inclusion criteria:

- 1. Successful manufacturing of at least 4 vials of Vigil.
- 2. One of the following:
 - a. Failure to meet the eligibility criteria for Protocol CL-PTL-119 due to i) histology of ovarian cancer and failure to achieve a complete clinical response following primary debulking surgery and standard paclitaxel/carboplatin therapy OR, ii) a histologic diagnosis of another gynecologic malignancy which is not ovarian cancer.
 - b. Recurrent ovarian cancer
 - c. Randomized on Protocol CL-PTL-119 and were subsequently unblinded at recurrence and were assigned to the placebo arm.
- 3. ECOG performance status (PS) \leq 1 (or \leq 2 due to carcinoid syndrome).
- 4. Estimated survival \geq 6 months.
- 5. Measureable per RECIST 1.1 or evaluable disease.
- 6. Adequate organ and bone marrow function as defined below:
 - a. Absolute neutrophil count (ANC) $\geq 1.5 \times 10^{9}/L$ (1500 per mm³)
 - b. Platelets ≥100 × 10⁹/L (100,000 per mm³)
 - c. Hemoglobin ≥9.0 g/dL (5.59 mmol/L)
 - d. Creatinine clearance (CrCL) >50 mL/min by the Cockcroft-Gault formula or by 24-hour urine collection for determination of creatinine clearance: Females:

CrCL (mL/min)

- e. Serum bilirubin ≤1.5 × upper limit of normal (ULN). This will not apply to patients with confirmed Gilbert's syndrome (persistent or recurrent hyperbilirubinemia that is predominantly unconjugated in the absence of evidence of hemolysis or hepatic pathology) who will be allowed in consultation with their physician.
- f. AST and ALT $\leq 2.5 \times$ ULN in patients with no liver metastasis

- g. AST or ALT ≤5 × ULN in patients with liver metastasis
- h. TSH within institutional limits. *If TSH is greater or less than institutional limits patients may participate if their T4 is within normal limits (WNL); patients may be on a stable dose of replacement thyroid medication; dose adjustments are allowed if needed*
- 7. Subject has recovered to CTCAE Grade 1 or better from all adverse events associated with prior therapy or surgery (or ≤ 2 due to carcinoid syndrome).
- 8. Pre-existing motor or sensory neurologic pathology or symptoms must be recovered to CTCAE Grade 2 or better
- 9. Patients with irreversible toxicity that is not reasonably expected to be exacerbated by the IPs (Vigil and/or atezolizumab) may be included (e.g., hearing loss) after consultation with the Principal Investigator
- 10. Subjects who are not rendered surgically sterile as a result of surgery for ovarian cancer, must have, negative urine or serum pregnancy test. If the urine test is positive or cannot be confirmed as negative, a negative serum test will be required for study entry.
- 11. Ability to understand and the willingness to sign a written informed protocol specific consent.
- 12. Willing and able to comply with the protocol for the duration of the study including undergoing treatment and scheduled visits and examinations including follow up.
- 13. Patients must have fully recovered from chemotherapy associated toxicities prior to starting treatment on this protocol.

Palliative radiotherapy is permitted provided:

- a. More than 3 weeks have elapsed between the end of radiotherapy and the first dose of study therapy, AND
- b. The irradiated lesion(s) (unless measurable progression after irradiation) cannot be used as target lesions.

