4. Estimated survival ≥ 6 months. 5. Measurable per RECIST 1.1 or evaluable disease. 6. Adequate organ and bone marrow function as defined below: a. Absolute neutrophil count (ANC) $\geq 1.5 \times 10^{9}$ /L (1500 per mm³) b. Platelets ≥100 × 10⁹/L (100,000 per mm³) c. Hemoglobin $\geq 9.0 \text{ g/dL} (5.59 \text{ mmol/L})$ d. Creatinine clearance (CrCL) >50 mL/min by the Cockcroft-Gault formula or by 24-hour urine collection for determination of creatinine clearance: Females: CrCL (mL/min) =Weight (kg) \times (140 – Age) \times 0.85 72 × serum creatinine (mg/dL) e. Serum bilirubin ≤1.5 × upper limit of normal (ULN). This will not apply to patients with confirmed Gilbert's syndrome (persistent or recurrent hyperbilirubinemia that is predominantly unconjugated in the absence of evidence of hemolysis or hepatic pathology) who will be allowed in consultation with their physician. f. AST and ALT ≤2.5 × ULN in patients with no liver metastasis g. AST or ALT $\leq 5 \times$ ULN in patients with liver metastasis h. TSH within institutional limits. If TSH is greater or less than institutional limits patients may participate if their T4 is within normal limits (WNL); patients may be on a stable dose of replacement thyroid medication; dose adjustments are allowed if needed 7. Subject has recovered to CTCAE Grade 1 or better from all adverse events associated with prior therapy or surgery (or ≤ 2 due to carcinoid syndrome) 8. Pre-existing motor or sensory neurologic pathology or symptoms must be recovered to CTCAE Grade 2 or better 9. Patients with irreversible toxicity that is not reasonably expected to be exacerbated by the IPs (Vigil and/or atezolizumab) may be included (e.g., hearing loss) after consultation with the Principal Investigator 10. Subjects who are not rendered surgically sterile as a result of surgery for ovarian cancer, must have, negative urine or serum pregnancy test. If the urine test is positive or cannot be confirmed as negative, a negative serum test will be required for study entry. 11. Ability to understand and the willingness to sign a written informed protocol specific consent. 12. Willing and able to comply with the protocol for the duration of the study including undergoing treatment and scheduled visits and examinations including follow up. 13. Patients must have fully recovered from chemotherapy associated toxicities prior to starting treatment on this protocol. Palliative radiotherapy is permitted provided: a. More than 3 weeks have elapsed between the end of radiotherapy and the first dose of study therapy, AND b. The irradiated lesion(s) (unless measurable progression after irradiation) cannot be used as target lesions.

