6.2.2 Dose Reduction / Escalation

Dose reduction or dose increase is not allowed for Vigil or atezolizumab.

Dose Holding Criteria

Both atezolizumab and Vigil should be held for any of the following AEs. Cycles held for toxicity should be made up (that cycle number is delayed rather than skipped). Atezolizumab and Vigil held may be resumed in patients whose AEs recover to Grade 0-1, with the exception of rash, which should recover to Grade 2 or better.

- Grade 2 pneumonitis
- Aspartate aminotransferase (AST) or alanine aminotransferase (ALT) greater than 3 and up to 5 times upper limit of normal (ULN) or total bilirubin greater than 1.5 and up to 3 times ULN
- Grade 2 or 3 diarrhea or colitis
- Symptomatic hypophysitis, adrenal insufficiency, hypothyroidism, hyperthyroidism, or Grade 3 or 4 hyperglycemia
- Grade 2 ocular inflammatory toxicity
- Grade 2 or 3 pancreatitis, or Grade 3 or 4 increases in amylase or lipase levels (greater than 2.0 times ULN)
- Grade 3 or 4 infection
- Grade 2 infusion-related reactions
- Grade 3 rash
- Grade 2 nephritis

Based on the mechanism of action of atezolizumab leading to T-cell activation and proliferation, there is the possibility of observing immune related Adverse Events (irAEs) during the conduct of this study. Potential irAEs include immune related colitis, pneumonitis, hepatitis, and endocrinopathies. Subjects should be monitored for signs and symptoms of irAEs. Subjects should be monitored for signs and symptoms of irAEs. In the absence of an alternate etiology (e.g., infection or PD) signs or symptoms of colitis, pneumonitis, hepatitis, and endocrinopathy should be considered to be immune-related.

Study Regimen Delay

- Cycles held for toxicity should be made up and not deleted.
- Dosing of atezolizumab and Vigil may be restarted when toxicity is ≤ Grade 1 severity with the exception of rash which may be ≤ Grade 2.
- In case of immune related adverse events, treatment with atezolizumab and Vigil may be delayed for up to 15 weeks (12 weeks for steroid therapy plus 3 weeks for gradual steroid tapering to a dose of ≤ 10 mg/day of prednisone.
- Subjects who delay treatment for more than 15 weeks due to toxicities will be considered off study treatment (see Section 6.3 Withdrawal).

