- Treatment delay not related to toxic events (including subjects unable to adhere to dose schedule) may not extend for more than three days unless due to symptoms related to disease or infection in which case up to a 4-week delay is allowed.
- If ≥ one 2-week delay due to disease or infection occurs, subject status must be reviewed by sponsor.

Atezolizumab should be permanently discontinued for any of the following AEs:

- Any life-threatening or Grade 4 AE
- Grade 3 or 4 pneumonitis
- Aspartate aminotransferase (AST) or alanine aminotransferase (ALT) >5 times upper limit of normal or total bilirubin >3 times upper limit of normal
- Diarrhea with abdominal pain, fever, ileus, or peritoneal signs; increase in stool frequency (Grade 4) stool incontinence, need for intravenous hydration for more than 24 hours, gastrointestinal hemorrhage, and gastrointestinal perforation
- Grade 4 hypophysitis
- Myasthenic syndrome/myasthenia gravis, Guillain-Barré or meningoencephalitis (all grades)
- Grade 3 or 4 ocular inflammatory toxicity
- Grade 4 or any grade of recurrent pancreatitis
- Grade 3 or 4 infusion-related reactions
- Grade 4 rash
- Grade 3 or 4 nephritis
- Myocarditis (all grades)

For combination treatment, the occurrence of a Grade 3 or 4 toxicity attributed to Vigil will result in the cessation of Vigil dosing and continuation of single agent atezolizumab only.

Please reference https://www.gene.com/download/pdf/tecentrig_prescribing.pdf for full prescribing information regarding atezolizumab.

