AESIs for atezolizumab include but are not limited to events with a potential inflammatory or immune-related mechanism and which may require more frequent monitoring and/or interventions such as steroids, immunosuppressants and/or hormone replacement therapy. These AESIs are being closely monitored in clinical studies with atezolizumab monotherapy and combination therapy. An immune-related adverse event (irAE) is defined as an adverse event that is associated with drug exposure and is consistent with an immune-related mechanism of action and where there is no clear alternate etiology. Serologic, immunologic, and histologic (biopsy) data, as appropriate, should be used to exclude alternate etiologies and support an irAE diagnosis. Appropriate efforts should be made to rule out neoplastic, infectious, metabolic, toxin, or other etiologic causes of the irAE.

If the Investigator has any questions in regards to an adverse event (AE) being an irAE, the Investigator should promptly contact the Medical Monitor.

AESIs for this study include the following:

- Cases of potential drug-induced liver injury that include an elevated ALT or AST in combination with either an elevated bilirubin or clinical jaundice, as defined by Hy's Law and based on the following observations:
 - Treatment-emergent ALT or AST > $3 \times$ baseline value in combination with total bilirubin > $2 \times$ ULN (of which $\ge 35\%$ is direct bilirubin)

- \circ Treatment-emergent ALT or AST > 3 \times baseline value in combination with clinical jaundice
- Suspected transmission of an infectious agent by the study treatment, as defined below

Any organism, virus, or infectious particle (e.g., prion protein transmitting transmissible spongiform encephalopathy), pathogenic or non-pathogenic, is considered an infectious agent. A transmission of an infectious agent may be suspected from clinical symptoms or laboratory findings that indicate an infection in a patient exposed to a medicinal product. This term applies only when a contamination of study treatment is suspected.

- Pneumonitis
- Colitis
- Endocrinopathies: diabetes mellitus, pancreatitis, adrenal insufficiency, hyperthyroidism, and hypophysitis
- Hepatitis, including AST or ALT > 10 × ULN
- Systemic lupus erythematosus
- Neurological disorders: Guillain-Barré syndrome, myasthenic syndrome or myasthenia gravis, and meningoencephalitis

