14.3 Risks Associated with Atezolizumab

Refer to the Atezolizumab Investigator's Brochure for a detailed description of anticipated safety risks for atezolizumab.

Systemic immune activation is a rare condition characterized by an excessive immune response. Given the mechanism of action of atezolizumab, systemic immune activation is considered a potential risk when given in combination with other immunomodulating agents. Systemic immune activation should be included in the differential diagnosis for patients who, in the absence of an alternative etiology, develop a sepsis-like syndrome after administration of atezolizumab, and the initial evaluation should include the following:

- CBC with peripheral smear
- PT, PTT, fibrinogen, and D-dimer
- Ferritin
- Triglycerides
- AST, ALT, and total bilirubin
- LDH
- Complete neurologic and abdominal examination (assess for hepatosplenomegaly)

If systemic immune activation is still suspected after the initial evaluation, contact the Medical Monitor for additional recommendations.

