¹² Serum Chemistry to include creatinine, glucose, total protein, blood urea nitrogen, total carbon dioxide, albumin, total bilirubin, alkaline phosphatase, and aspartate transaminase and/or alanine transaminase and electrolytes (total calcium, chloride, potassium, sodium).

1 cycle = 3 weeks	Pre-Study ¹	Screening	Cycle 1	Cycle 2	Cycles 3, 6, 9, 12	Cycles 4, 5, 7, 8, 10, 11	EOT (30 days) ²	Response Follow-Up (quarterly) ³	Survival (3 years) ⁴
Visit Window		-2 weeks			±5 days			+/- 7 days	±4 weeks
CA-125 ¹³	Х	Х	Х	Х	Х	Х	Х	Х	Х
TSH ¹⁴		Х			Х				
Pregnancy Test (if applicable)		Х							
Immune Function Analysis ¹⁵	≤ 1 week of tumor procurement	x			х		х	х	
Tissue Procurement	Х								
Vigil Administration ¹⁶			Part 1: Both Part 2: Vigil or Atezolizumab		Х	Х			
Atezolizumab Administration ¹⁷					Х	Х			
Site Injection Assessment ¹⁸			х	X	Х	Х			
Tumor Biopsy					X ¹⁹				
Phone Contact	Х								Х

Version: 04 Effective: 26-SEP-2018

¹³ Obtain results from medical records when available.

¹⁴ TSH will be collected at screening and every third cycle thereafter.

¹⁵ Immune Function Analysis sample will be collected at baseline, prior to study agent administration at Cycle 3 and every 3 cycles thereafter.

¹⁶ Vigil Administration every 3 weeks on Day 1 as long as sufficient material is available and patient is deemed appropriate to continue. When combined, Vigil should be administered first, followed 30 minutes (+/- 5 min) later by atezolizumab.

¹⁷ Atezolizumab is to be administered at a dose of 1200 mg as an intravenous infusion on Day 1 every 3 weeks. The initial dose is to be administered over one hour and if well tolerated, subsequent infusions may be administered over 30 minutes.

¹⁸ Assessment of injection site will occur during the Vigil post-dose observation period and through 24 hours after Vigil dosing through patient contact.

¹⁹ Tumor biopsy for correlative studies including scoring of tumor infiltrating lymphocyte (TIL) and PD-1 / PD-L1 expression analysis will be obtained at tissue procurement, prior to Cycle 3 combination dosing (for individuals in Part 2) and at any time after the end of Cycle 3.

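### Criterion 6g caps only one of AST and ALT in subjects with liver metastasis, and the routine chemistry panel accepts one enzyme although five on-treatment triggers depend on either

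*Combined protocol and SAP*

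**What the plan says.** **Entry.** Section 5.4 gives two aminotransferase limits. Criterion 6f covers subjects without liver metastasis and requires both AST and ALT at or below 2.5 × ULN. Criterion 6g reads "AST or ALT ≤5 × ULN in patients with liver metastasis". The synopsis has the same contrast, one criterion directly after the other: "AST and ALT ≤2.5 × ULN in patients with no liver metastasis g. AST or ALT", followed by the 5 × ULN limit.

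**Routine measurement.** Footnote 12 of Appendix B (Parts 1 and 2) and of Appendix C (Part 3) lists the contents of serum chemistry, among them "aspartate transaminase and/or alanine transaminase and electrolytes".

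**On-treatment rules.** All of these depend on either enzyme:
- Section 6.2.2, hold both agents: AST or ALT "greater than 3 and up to 5 times upper limit of normal".
- Section 6.2.2, stop atezolizumab permanently: AST or ALT above "5 times upper limit of normal or total bilirubin" above 3 × ULN.
- Section 14.0, two liver-injury AESIs, both beginning "Treatment-emergent ALT or AST": above 3 × baseline together with total bilirubin above 2 × ULN, or together with clinical jaundice.
- Section 14.0, hepatitis AESI: "Hepatitis, including AST or ALT" above 10 × ULN.

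Section 14.3 lists "AST, ALT, and total bilirubin" in the work-up of suspected systemic immune activation. That is the only on-treatment place where both enzymes are asked for, and it is not routine.

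**The concern.** There are two separate gaps. The 'or' in 6g means that one acceptable enzyme satisfies the criterion whatever the other is, so entry is possible above the level that the protocol treats as too high for continued atezolizumab. The 'and/or' in footnote 12 means that a site can follow the schedule in full and never see the enzyme that would have triggered a rule.

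Safety of the combination is the primary objective. Section 16.1 builds the safety evaluation on AEs, AESIs, SAEs and laboratory changes from baseline, in about 20 to 25 subjects. Hepatitis is a named atezolizumab risk. In a trial this small, one missed hepatic event matters both to the subject and to the description of tolerability. Part 3 is the more exposed: the toxicity row in Appendix C is limited to AESIs and SAEs, and three of the five triggers are AESIs.

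**Working it through.** The plan gives no figure to reproduce. The check sets the entry rule and the panel against the on-treatment rules. All enzyme values below are assumed for illustration.

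**1. Entry rule against stop rule.** Take a subject with liver metastasis, AST 8 × ULN and ALT 3 × ULN.
- 6g as written: (8 ≤ 5, false) or (3 ≤ 5, true) = eligible.
- Enzyme level in the stop rule: (8 > 5, true) or (3 > 5, false) = exceeded. AST is at 8/5 = 1.6 times that level.
- 6g with 'and': false and true = not eligible.

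In general, the negation of 'AST or ALT above 5 × ULN' is 'AST and ALT at or below 5 × ULN'. With 'and', 6g is the exact complement of the enzyme limb of the stop rule. With 'or', it is not.

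**2. Panel against triggers.** Either-enzyme triggers: hold 1 + stop 1 + liver-injury AESIs 2 + hepatitis threshold 1 = 5. Suppose that a site measures ALT only, as footnote 12 permits, and ALT is 2 × ULN:

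| Unmeasured AST | Trigger met on AST | Seen from ALT alone? |
|---|---|---|
| 4 × ULN | hold (above 3, up to 5) | no |
| 6 × ULN (6/5 = 1.2 times the stop level) | stop (above 5) | no |
| 11 × ULN | hepatitis threshold (above 10); stop level also exceeded | no |

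The two liver-injury AESIs compare with baseline, so they need each enzyme at baseline as well as on treatment.

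**3. Who is exposed, and when.**
- Without liver metastasis: 6f cannot be confirmed without both enzymes, and under section 6.1 the sponsor checks source documents against the criteria before confirming eligibility. Both baseline values should therefore exist. The gap is on treatment only.
- With liver metastasis: neither 6g nor footnote 12 requires the second enzyme. The gap is at entry and on treatment, and the second enzyme may have no baseline.

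**4. Extra results if both enzymes are required.** Scheduled serum chemistry in Appendix B, leaving out the pre-study sample (footnote 1 lets it come from medical records):
- Cycles 1 to 12: 1 + 1 + 4 + 6 = 12. End of treatment: 1. Total 13.
- Screening adds 1 where 6f does not already require both: 13 + 1 = 14.
- Upper bounds if every enrolment completes 12 cycles and every site runs one enzyme: 13 × 20 = 260 to 13 × 25 = 325 if no subject has liver metastasis; 14 × 20 = 280 to 14 × 25 = 350 if all do.

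The count is per enrolment, because the protocol allows re-procurement and re-enrolment into Part 2. Part 3 adds one result per further cycle.

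**The case against.** The strongest reply is that 6g is loose drafting. It belongs to a list meant to establish adequate organ function, and leaving one enzyme without a ceiling defeats that purpose. Registration review (section 6.1), the discretionary exclusions (section 5.3 item 7 and section 5.5 item 7) and Medical Monitor approval before Vigil is shipped (section 10.2) also stand in the way. On treatment, many sites may run both enzymes anyway, and hepatitis is to be managed under the package insert, which might ask for both.

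Part of this stands. The drafting explanation is plausible, and some cases would probably be caught. But the reviews test against the criteria as written, and judgement can act only on a value that was measured. What the package insert requires cannot be checked from the documents, which is why the point is confined to the protocol's own schedule.

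Three stronger readings are tempting, and the documents do not support them:
- A reader might infer that an unmeasured rise leads to no hold, no stop and no AESI report. The hold and stop rules each have a bilirubin limb that needs no enzyme. Hepatitis is itself an AESI, with the 10 × ULN threshold only included in it. Section 6.2.2 treats signs or symptoms of hepatitis without another cause as immune-related, and section 5.6 ends treatment for autoimmune reactions of Grade 3 or above. What is lost is detection of an enzyme rise without those features.
- A reader might infer that every subject at a one-enzyme site lacks a baseline for the other enzyme. Criterion 6f rules this out for subjects without liver metastasis, if it is followed.
- A reader might infer that a subject entering above 5 × ULN must be stopped at once. The stop list applies to AEs, and section 14.5 does not require an unchanged pre-existing condition to be reported as one. The protocol leaves the handling of such a subject unclear.

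**Conclusion.** The point holds as two wording defects with safety consequences. Criterion 6g, read literally, sets no upper limit on the second enzyme in subjects with liver metastasis and so can admit a subject above the atezolizumab stop level. Footnote 12 lets one enzyme satisfy routine chemistry in all three parts, so under the protocol schedule alone the enzyme limb of any of five triggers can go unseen.

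The text is clear; how often it matters is not. The documents do not say how many subjects have liver metastasis, how many sites run one enzyme, or how often AST and ALT differ enough to matter. The number affected may be zero. The conclusion rests on taking 'or' and 'and/or' at face value, which is reasonable because the neighbouring 6f says 'and'. The correction should be made: it is cheap and brings the measurements into line with the protocol's own safety rules.

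**What to change.** Two independent changes:
1. In section 5.4 and the synopsis, reword 6g as: AST and ALT ≤5 × ULN in patients with liver metastasis. This settles entry, and by itself obliges sites to have both results at screening.
2. In footnote 12 of Appendices B and C, replace 'and/or' with 'and' between the two enzymes. This settles on-treatment monitoring.

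Neither change depends on the other.

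**Cost.** Amendment wording. A subject with liver metastasis and one enzyme above 5 × ULN would no longer qualify. Sites that run one enzyme add one result per scheduled chemistry from blood already drawn: up to 13 per enrolment in Parts 1 and 2 without liver metastasis, 14 with, and one more per Part 3 cycle. Sites that already run both add nothing.

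**Limit.** Subjects with liver metastasis could still enter between 3 and 5 × ULN, inside the hold band. These changes do not address that.
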